Music may have a positive impact on pain and distress for children undergoing intravenous placement. Benefits were also observed for the parents and health care providers.

This study uses similar methods and looked for similar outcomes as Music:Ed, but using recorded rather than live music, and in a non-emergency setting.

The Music:ED study will therefore use a controlled experimental design to investigate the impact of using therapeutic live music in the Alder Hey Paediatric Emergency Department to reduce pain and distress during interventional procedures.

The outcomes of the study will provide evidence for the use of live music in the PED to support and enhance patient experience. Distress is often particularly high within the emergency department. If a patient's experience whilst attending the Emergency Department can be less traumatic, this will be of benefit to all: patients, families and clinicians. A patient who is less distressed is more cooperative and may be easier and quicker to treat.

Methodology and Methods

Research Question

Does live music decrease the pain and distress of patients undergoing a procedure within the paediatric emergency department?

Aims of the Study

Our aims/objectives include:

1. To explore whether live music helps to decrease pain and distress in patients in the Paediatric Emergency Department
2. To explore whether procedures can be carried out with greater ease from a clinician's perspective and whether staff experience of the situation is impacted by the presence of live music.
3. Exploring the overall impact on the ED experience from the patients, families and clinicians' perspectives.

Methodological Approach

We have chosen a mixed method design to provide us with different forms of data and insights from multiple practitioner, parent and patient perspectives throughout the experience.

Quantitative data includes collecting information about the patient's pain levels and qualitative data will be collected from open response questionnaires to explore patient distress and the practitioner, parent and patient perspectives on the experience.

Methods

There will be an experimental (live music) and a control (no live music) group.

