This is suitable for children age 3+. As children self-report, the Research Nurse will collect this data on a paper CRF. Wong Baker scores will be collected before, during and after the procedure. If mid-procedure collection of pain score is inappropriate, then participants can be asked about mid-procedure pain scores after the procedure.

A self-reported pain score will also be taken in advance, during the recruitment process, to provide a baseline measure.

2. Quantitative: Observed pain.

Data will be collected on observed pain levels using a validated observational tool: Faces, Legs, Activity, Cry and Consolability (FLACC) pain assessment tool.

This tool is suitable and validated for all ages of the recruited participants, from 6 months until 16 years. References regarding justification of this scale for these age ranges are below.^{5 6}

Scoring will take place before, during and after the procedure.

The Research Nurse will carry out this scoring, and when available, an independent observer from the Emergency Department staff will also. The Research Nurse will collect this data on the paper CRF.

Heart rate will also be monitored throughout, where a child is cooperative enough. HR will be noted approximately every two minutes before, during and after procedure, (cleaning marks the beginning of the procedure, final bandage/dressing marks the completion). The Research Nurse will note HR data on the CRF. There will be an option for the Research Nurse to record 'not available' for heart rate measurements either because child refuses or because of probe or monitor issues etc.

3. Qualitative: Distress and experiences of patients, families and clinicians.

Our outcome measures will include collecting qualitative information on patient's distress, and patients', families' and clinician's Emergency Department experience. All recruited patients will receive a paper questionnaire with open text response options.

Qualitative questions for Experimental AND Control Groups:

The following two questions will be asked of both the experimental (live music) AND control (no live music) groups. The questions will be asked of each of these two people: patient and parent/legal guardian.

'Please answer the following questions, in particular, in regard to distress levels/lack of distress':

- Qualitative question 1. What do you think helped you/your child during their procedure?

- Qualitative question 2. Did anything make the situation worse?

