Record the duration of the procedure (cleaning marks the beginning of the procedure, final bandage/dressing marks the completion)

Record how many attempts were required to carry out procedure

Record the role and grade of the Clinician carrying out the procedure

Record heart rate at 2-minute intervals if tolerated. Include option for the research nurse to record 'not available' for heart rate measurements either because child refuses or if probe or monitor issues etc

Is there an independent observer present? If so, who?

Inclusion criteria

Parent/Legal Guardian present and able to consent.

Age range: 6 months - 16 years. (see references at end notes 5&6 below)

Procedures: Capillary blood sampling, cannulation, venepuncture, suturing, wound cleaning and closure.

Families and children whose primary language is other than English will be included in the study if their English speaking skills are at a level that they can understand and complete the consent/assent process.

Exclusion criteria

Children with Special Educational Needs, children with global development delay, sensory impairments, neurological deficits or disorders, impairment to pain i.e. spina bifida.

Children in resuscitation or unconscious.

Non-English speaking.

Suspected ingestion of recreational drugs, antidepressants or alcohol

Concerns relating to NAI (non accidental injury)/safeguarding concerns

Life or limb critical injuries

Children too unwell to participate

Recruitment

Research Nurses will identify appropriate patients using a screening tool that will outline the inclusion/exclusion criteria. For inclusion in either group, a parent or legal guardian must be available to give consent, collected by the Research Nurse.

The Research Nurse will introduce the study to potential recruits, and supply and explain Participant Information Sheets. Posters will be displayed within Alder Hey's Emergency Department to promote the study and give some initial details.

The same number of participants will be recruited to the control (no live music) group as a comparison, on days that the musicians are not in the department. All patients in both groups will continue to receive standard care. Each child can only be in the study once and for one procedure. Patients will be free to withdraw from the study at any time.

Ethics and governance

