Quantitative data will be entered into SPSS. We will analyse the data using the chi-square test for trend, paired samples t-tests and Wilcoxon sign ranks tests as appropriate. Participants with missing data (either before procedure or after procedure) will be excluded from analysis. NVivo 10 Software will be used to assist in the organization and coding of qualitative data (e.g. free text open question responses). Qualitative thematic analysis will be interpretive and iterative. Our approach to synthesizing qualitative and quantitative data will draw on the constant comparative method.

Dissemination

Findings from the study will be disseminated to professionals and to children and their families. Dissemination potentially includes publication in journals and via presentation at conferences and at practice development workshops. This will be done locally through the associated universities and hospitals as well as potentially internationally. By working with colleagues in clinical practice on an on-going basis throughout the study, the researchers anticipate that the study will have a direct impact on practice.

Benefit to patients

Findings will be used to further our understanding of the potential benefits of using live music within the Paediatric Emergency Department, with an aim to improve patient experience.

Link to Alder Hey Research & Universities' Strategies

Alder Hey Children's Hospital's strategy is to build a healthier future for children and young people. One of Alder Hey's main aims is to 'ensure all of our patients and their families have a positive experience whilst in our care'. This study very much follows this ethos, by exploring ways to make the hospital experience a less traumatic one.

A key strength of the University of Liverpool's research strategy is its impact intensive approach. The design of this study will explore ways of making immediate, effective improvements to the care of children and young people.

References:

¹ A. Y. R. Kühlmann(2018) *Meta - analysis evaluating music interventions for anxiety and pain in surgery*. Available at 002 <https://onlinelibrary.wiley.com/doi/abs/10.1/bjs.10853>

² Kari Sand-Jecklin, EdD, MSN, RN, AHN-BC, Howard Emerson, BA, CMP (2010) *The Impact of a Live Therapeutic Music Intervention on Patients' Experience of Pain, Anxiety, and Muscle Tension* *Holist Nurs Pract* 2010;24(1):7–15

³ *J Dev Behav Pediatr.* 2007 Oct;28(5):399-403.

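### Groups are formed by day without randomisation, but the named tests cannot adjust the music-control comparison for procedure or age

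*Protocol*

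**What the plan says.** The Research Question is a comparison between groups: "Does live music decrease the pain and distress of patients undergoing a procedure within the paediatric emergency department". Under Methods and again under Recruitment, an equal number of controls is recruited "as a comparison, on days that the musicians are not in the department". No randomisation, matching or stratification is described for this study.

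Inclusion criteria admit children from 6 months to 16 years and a mixed list: "Procedures: Capillary blood sampling, cannulation, venepuncture, suturing, wound cleaning and closure". Methods estimates 60 to 80 children per group.

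For analysis, the Data Analysis section says: "We will analyse the data using the chi-square test for trend, paired samples t-tests and Wilcoxon sign ranks tests as appropriate". No other method for the quantitative data is named.

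On baseline pain, Methods of data collection and analysis says of Wong-Baker (age 3 and over): "A self-reported pain score will also be taken in advance, during the recruitment process, to provide a baseline measure". For FLACC (all ages) it says: "Scoring will take place before, during and after the procedure". It does not say whether the first FLACC score precedes the music.

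**The concern.** Only a contrast of music with control answers the research question. Paired t-tests and signed-rank tests show whether pain changed over time within children; they do not compare the two groups. The chi-square test for trend can compare them, but without covariates. None of the three can account for procedure or age, although age is on the CRF list.

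Because the calendar assigns the groups, nothing makes music days and control days alike in which procedures are done or how old the children are. Comparing pre-post change does not solve this. Change scores remove stable differences in starting level, but not differences in how much pain each procedure causes.

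The result is meant to count. Value of the study says: "The outcomes of the study will provide evidence for the use of live music in the PED". Under Dissemination, "the researchers anticipate that the study will have a direct impact on practice".

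**Working it through.** The protocol gives no effect size, SD, significance level or power, so there is no figure of its own to reproduce. The 60 to 80 per group is a recruitment estimate. The rest is an illustration.

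**Inputs**
- From the protocol: n = 60 or 80 per group; several procedures; allocation by day.
- Assumed: two procedure types whose mean pain differs by a gap g of 0.5 to 1.0 within-procedure SD; a systematic difference of 10 to 20 percentage points between the groups in the share having the more painful type; average mix 50:50 unless stated; no true music effect; unadjusted two-sample test at two-sided 5%.

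**Bias** = g × mix difference, in within-procedure SD:
- 0.5 × 0.10 = 0.05
- 0.5 × 0.20 = 0.10, or 1.0 × 0.10 = 0.10
- 1.0 × 0.20 = 0.20

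**Total SD** = sqrt(1 + g² × mean of p(1−p)), where p is each group's share of the more painful type. At g = 1.0 and mix 40% v 60%, this is sqrt(1 + 0.24) = 1.114, so a bias of 0.20 is 0.20/1.114 = 0.180 total SD.

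**False-positive rate** (noncentral t, noncentrality = bias / (total SD × sqrt(2/n))):

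| Bias | Gap, mix | n = 60 | n = 80 |
|---|---|---|---|
| 0.05 | 0.5, 45% v 55% | 5.8% | 6.1% |
| 0.10 | 1.0, 45% v 55% | 7.8% | 8.7% |
| 0.10 | 0.5, 40% v 60% | 8.2% | 9.4% |
| 0.20 | 1.0, 40% v 60% | 16.4% | 20.4% |
| 0.20 | 1.0, 20% v 40% | 16.8% | 20.9% |

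**Does adjustment repair it?** Simulation with 20,000 runs, pre-post correlation 0.5, g = 1.0, music 40% v control 60%, no music effect (n = 60/80):

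| Analysis | Bias | Rejection | SE |
|---|---|---|---|
| Unadjusted | −0.20 | 15.9% / 20.8% | 0.203 / 0.176 |
| Adjusted for procedure | 0.00 | 4.9% / 4.9% | 0.187 / 0.162 |
| Adjusted for procedure and pre-score | 0.00 | 4.8% / 4.8% | 0.163 / 0.140 |

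**Hiding an effect** (normal approximation). Take a true benefit of 0.5 SD, g = 1.0 and a 60/40 mix against music. The net difference is 0.5 − 0.2 = 0.3 SD. Power falls from 69% to 31% at n = 60, and from 81% to 40% at n = 80.

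**Separate paired tests in each group.** Suppose both groups truly change by the same 0.2 to 0.4 SD and each test has power p. Exactly one group is then significant with probability 2p(1−p): 22% to 50% at n = 60, and 10% to 49% at n = 80. One significant group and one non-significant group is therefore no evidence of a music effect.

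**Why the timing of the baseline matters.** A question put to the music group asks how music affected distress before the procedure, so music may start before the first FLACC score. Assume music has already lowered that score by 0.1 to 0.2 SD, the pre-post slope is 0.5 and the total effect is 0.4 SD. Adjusting for the score then removes 0.5 × 0.1/0.4 = 12.5% to 0.5 × 0.2/0.4 = 25% of the effect.

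**The case against.** The strongest reply is that covariates and baseline definitions usually belong in a statistical analysis plan, which may exist unseen, and that the words on appropriateness leave room. That would answer a protocol that was silent. This one lists its tests, and the natural reading is a choice among those three. None gives an adjusted group comparison.

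Nor do the documents show that the mix differs between days. Both groups recruit from January to March 2019 under the same criteria and screening tool, and all eligible children are sought while the musicians are present. This limits seasonal and selection differences, but balances neither procedure nor age across days.

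The size is wholly assumed. With a 50:50 mix, chance alone gives a mix difference with SD sqrt(2 × 0.25/n), about 9 points at n = 60 and 8 at n = 80, so 10 points is unremarkable even in a randomised trial. That is fair, and the low end is small. But randomisation makes such differences part of the 5% error rate; a systematic difference between days is not covered.

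The study is a pilot with exploratory aims, and the expected impact on practice is tied to ongoing work with clinical colleagues. This lowers the severity. The stated intention to provide evidence for live music remains.

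On data capture, the printed CRF list has no line for the procedure performed or the recruitment date. The list need not be exhaustive, the screening tool covers the eligible procedures, and medical records are accessible. These data are not shown to be lost; the list merely does not assure them.

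**Conclusion.** The concern holds. The design is non-randomised and allocated by day, the question is between groups, and the listed tests are either within-child or unadjusted. Following Data Analysis as written, a procedure or age difference between days enters the pain result.

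Under the assumed gaps and mixes, the bias is 0.05 to 0.20 within-procedure SD and the false-positive rate about 6% to 20% against a nominal 5%. The age contribution was not quantified. The change should be made. Confidence is medium, because the direction and size of any real mix difference are unknown. Adjustment will not remove unmeasured differences between days.

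**What to change.** **In Data Analysis**, state that the music-control difference in pain is estimated by regression adjusted for age, procedure type and a pain score taken before music starts. Show the unadjusted difference alongside and describe the result as non-randomised. Linear or ordinal form can be left to the analysis plan.

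- **Baseline:** for age 3 and over, use the Wong-Baker score from recruitment. Use FLACC as a baseline only if the data-collection text is changed to time the first FLACC before the musicians start. Otherwise omit it, adjust children under 3 for age and procedure only, and say how the two age bands are combined.
- **Other covariates:** adjust for analgesia or local anaesthetic only where the record shows it was given before music. Do not adjust for Entonox, other distraction, attempts or duration, which music may change.
- **CRF safeguard:** add the procedure performed, the recruitment date, and the timing of analgesia and local anaesthetic.
- **Secondary:** if scores correlate within day, use standard errors that allow for day, with a small-sample correction.

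**Cost.** Two CRF lines, two timing ticks, the timing of the first FLACC, wording, a little more analysis work, and no extra patients. If procedure is unrelated to pain, a 20-point mix difference (group-procedure correlation 0.2) widens intervals by sqrt(1/(1 − 0.04)) − 1 = 2.1%. If it is related, intervals narrow: in the simulation at n = 60 the SE falls from 0.203 to 0.187, about 8%.

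Allowing for day costs more. Widening = sqrt(1 + (m−1)ICC) × t(day df)/t(child df) − 1, with m children per day and intraclass correlation ICC. The numbers of days and the ICCs are assumed:

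| Days per group, m | ICC 0 | ICC 0.05 | ICC 0.10 |
|---|---|---|---|
| 16, m = 4 / 5 | 3.2 / 3.4% | 10.7 / 13.3% | 17.7 / 22.3% |
| 8, m = 8 / 10 | 8.4 / 8.6% | 25.9 / 30.8% | 41.3 / 49.7% |

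These figures use day-level degrees of freedom, the conservative end.

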2. By 2020 AHCH plans to be a world class, child-focused centre of research, innovation and education expertise to improve the health and wellbeing outcomes for children and young people. Supporting patients through stressful and invasive procedures is crucial. Inspired by the patients and families that we care for, this research fits well with the AHCH vision, demonstrating an innovative and evidence-informed approach to enhancing practice.
3. The University of Liverpool's impact intensive approach to research is a key strength. This study is designed to have a positive immediate impact on the children and young people participating and those undergoing interventional procedures in the future, helping to enhance patient experience of the ED.

Value of the study

There is a growing evidence-base for the use of music in healthcare settings, with music already demonstrated to reduce stress, distress and the perception of pain in some clinical contexts^{1 2}. Yet, there is a lack of studies examining the impact of live music in paediatric emergency contexts.

A literature review revealed that there is a lack of studies examining the impact of live music in paediatric emergency contexts.

Related studies either used recorded music in the place of live music, or, if live music was used, then it was within a non-emergency setting.

Prior related studies include:

*'Interactive music as a treatment for pain and stress in children during venipuncture: a randomized prospective study.'*³

This controlled study demonstrates that songs and music, performed by "professional" musicians, have a beneficial effect in reducing distress before, during, and after blood tests. This study shows, moreover, that the presence of musicians has a minor, but yet significant, effect on pain due to needle insertion.'

This study uses similar methods and looked for similar outcomes as Music:ED, but in a non-emergency setting

*'Music to reduce pain and distress in the pediatric emergency department: a randomized clinical trial.'*⁴

Health care providers reported that it was easier to perform the procedure for children in the music group (76% very easy) vs the standard care group (38% very easy) (P = .03). Health care providers were more satisfied with the intravenous placement in the music group (86% very satisfied) compared with the standard care group (48%) (P = .02).

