Research Nurses will identify appropriate patients using a screening tool that will outline the inclusion/exclusion criteria. Participant Information Sheets (PIS) will be provided to patients and their families for their appropriate ages. They will be offered a copy of the results if they would like and will be told how the results will be reported when the study is completed.

After gaining written consent from the parent and written or verbal assent from the child, Wong-Baker pain scoring methods will be explained in advance of the procedure. Necessary data will be collected for the CRF.

The participant's involvement in the study will be limited to the length of time of their Emergency Department visit, so will be just one day and one procedure.

For the experimental (music) group, Cascade's musicians will spend eight weeks, twelve hours per week in the ED and will aim to recruit all eligible children during that period. As this is a pilot study recruitment targets need to remain flexible, but are estimated at 60-80 participants (per group).

The same number of participants will be recruited to the control (no live music) group as a comparison, on days that the musicians are not in the department. All patients in both groups will continue to receive standard care. Each child can only be in the study once and for one procedure. Patients will be free to withdraw from the study at any time.

Following the procedure and interviews, patients involved will be offered a sticker and a CD of calming music recorded by Cascade Music as a thank you for their participation. For ethical reasons, this will not be mentioned in advance.

Timeline:

December 2018:

Implementation of study including finalising ethical approval

Recruitment of Research Nurse,

Publicise study within Alder Hey Children's Hospital's Emergency Department.

January - March 2019:

Recruitment of participants to the study, both experimental (music) and control (non-music) groups.

Data collection from participants.

March - May 2019:

Complete data analysis

Write report

Explore dissemination options including publishing and conferences

Plan next funding application

Methods of data collection and analysis

Three sets of data will be collected:

1. Quantitative: Self-reported pain.

A validated observational tool will be used: Wong Baker Faces.

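### None of the named tests yields a music-control difference in pain points, so the pilot's main between-group result should be stated as an estimate with a 95% confidence interval

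*Protocol*

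**What the plan says.** The Research Question asks whether live music reduces pain and distress during procedures, and the first aim is exploratory: "To explore whether live music helps to decrease pain and distress in patients in the Paediatric Emergency Department". The Methods section sets up an experimental and a control group. On size it says: "As this is a pilot study recruitment targets need to remain flexible, but are estimated at 60-80 participants (per group"). On the comparison group it says: "The same number of participants will be recruited to the control (no live music) group as a comparison". Controls are enrolled on days without musicians, each child takes part once, and no matching of children across groups is described.

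The quantitative analysis is one sentence in Data Analysis: "We will analyse the data using the chi-square test for trend, paired samples t-tests and Wilcoxon sign ranks tests as appropriate". The next sentence is a complete-case rule: "Participants with missing data (either before procedure or after procedure) will be excluded from analysis". Pain is scored before, during and after the procedure, by self-report (Wong-Baker) and by observation (FLACC). Of the self-report scale the protocol says "This is suitable for children age 3" and above, while enrolment starts at 6 months. The Timeline ends with planning a further funding application.

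**The concern.** The study has a two-group question, but two of its three named methods are one-group methods. Pain around a procedure can rise and fall whether or not music is played, so a significant before-after change within the music group is not evidence about music. The only named method that can set music against control gives a p-value without a size.

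Two uses of the result suffer. A clinician reading the report would not learn by how many points the groups differed, or how uncertain that is. Whoever plans the next study would lack the two quantities needed to size it: a plausible range for the difference, and the SD in each group.

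**Working it through.** **1. What each named method delivers**

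| Method | Compares | Effect in pain points, music vs control |
|---|---|---|
| Paired t-test | before vs after, same child | none (gives a mean change within one group) |
| Wilcoxon signed rank | before vs after, same child | none |
| Chi-square test for trend | the two groups across ordered scores | none (p-value only) |

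A within-group test can be significant with no music effect at all. Suppose pain changes by 0.5 SD (of the change score) in both groups alike, which is an assumption for illustration. Power of each paired test ≈ Φ(0.5·√n − 1.96). At n = 60 this is Φ(3.87 − 1.96) = 97%; at n = 80 it is Φ(4.47 − 1.96) = 99%. Both groups would very probably show significant change while the difference between them is zero.

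**2. The plan's own figure**

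The 60 to 80 per group (120 to 160 in total) cannot be reproduced. No significance level, power, effect size or SD is given. The figure stands beside the musicians' time in the department, eight weeks at twelve hours (8 × 12 = 96 hours).

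**3. What a between-group p-value can show at that size**

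Inputs: n = 60 and 80 per group (Methods). Assumed: two-sided 5%, independent children, difference d = 0.2 to 0.5 SD. Formula: power ≈ Φ(d·√(n/2) − 1.96). A chi-square test for trend on ordered scores has about the power of this comparison of means.

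| d (SD) | n = 60 | n = 80 |
|---|---|---|
| 0.2 | Φ(1.095 − 1.96) = 19% | Φ(1.265 − 1.96) = 24% |
| 0.3 | Φ(1.643 − 1.96) = 38% | Φ(1.897 − 1.96) = 48% |
| 0.4 | Φ(2.191 − 1.96) = 59% | Φ(2.530 − 1.96) = 72% |
| 0.5 | Φ(2.739 − 1.96) = 78% | Φ(3.162 − 1.96) = 89% |

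The noncentral t distribution agrees within one percentage point. Power reaches 50% where d = 1.96·√(2/n), that is 0.36 SD at n = 60 and 0.31 SD at n = 80.

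If the complete-case rule removes 10-20% of children (assumed; n from 60 × 0.8 = 48 to 80 × 0.9 = 72), power is 16-22% at 0.2 SD and 31-44% at 0.3 SD.

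**4. What an interval would show instead**

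Half-width of the 95% interval = 1.96·√(2/n) SD.

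- n = 60: 1.96 × 0.1826 = 0.36 SD. n = 80: 1.96 × 0.1581 = 0.31 SD.
- After 10-20% exclusions (n = 48 to 72): 0.40 to 0.33 SD.
- Self-report: the share aged 3 or over is not given. At 60% (n = 36 to 48) the half-width is 0.46 to 0.40 SD; at 90% (n = 54 to 72) it is 0.38 to 0.33 SD.

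**5. Why the next study needs the estimate**

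Size per group for 80% power = 2(1.96 + 0.842)²/d² = 15.7/d². This gives 393 at 0.2 SD, 175 at 0.3, 99 at 0.4 and 63 at 0.5, a sixfold range (393/63 = 6.2). A p-value does not say where in that range to plan.

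**The case against.** The strongest reply is that naming tests does not rule out estimates, and that reporting them is commonly left to a statistical analysis plan, which is not at hand. It is correct that estimates are unstated and not excluded. But the protocol did choose its methods, and the chosen set does not fit the two-group question. That is a poor choice of method and not merely a detail left for later. The words allowing choice as appropriate select among the three tests and add no between-group estimate.

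A second reply is that a pilot need not be powered. This stands: the flexible size is openly stated and is not the fault here.

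Some stronger readings are tempting, and the protocol does not support them.

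- A reader might infer that the study would most likely miss an effect like the one in its live-music precedent. Value of the study says of that study that "the presence of musicians has a minor, but yet significant, effect on pain due to needle insertion", but gives no size or SD, and the effect was detected there. At 0.4 SD this pilot would be more likely than not to find significance. Adjusting for a baseline score correlated 0.5 with the outcome (assumed) would raise power to 24-31% at 0.2 SD and 48-59% at 0.3.
- A reader might infer that the whole question is answered by significance tests. The design is mixed-method: distress is assigned to qualitative data, with thematic analysis and a synthesis of both strands.
- A reader might see a conflict between a pilot and the Dissemination statement that "the researchers anticipate that the study will have a direct impact on practice". The full sentence ties that hope to working with clinical colleagues during the study, and the aims are worded as exploration. No section says that a non-significant result will be read as no effect.

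**Conclusion.** The point holds as a fault in the choice of analysis. Of the three named methods, two cannot compare music with control, and the third gives no difference in pain points. The size of the problem depends on an effect the protocol does not state. Below about 0.31 to 0.36 SD, a between-group test at 60 to 80 per group is more likely than not to be non-significant; at 0.4 SD or more the reverse holds. This assumes a two-sided 5% level, independent children, no baseline adjustment and no exclusions.

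An interval with a half-width of about a third of an SD would be informative in either case. It has a limit of its own: groups are formed by day of attendance and not by randomisation, so differences between music days and other days in staff or case mix lie outside it. The point calls for a change to Data Analysis only. It gives no ground for rewording Dissemination or enlarging the pilot.

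**What to change.** Add to Data Analysis, in words such as:

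> For each pain score, the main result is the estimated difference between the music and control groups, in points, with its 95% confidence interval, from a between-group comparison, together with the standard deviation in each group. P-values and within-group tests are secondary. Because groups were formed by day of attendance and not by randomisation, the confidence interval does not cover confounding, and the report will say so.

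It would help to state the expected precision beside it: a half-width of about 0.36 to 0.31 SD at 60 to 80 per group, wider for self-report because of the age limit.

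The cost is a few sentences and a little more analysis work with data already planned; no more children are needed. The stated claim becomes more modest.
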